Study Population and Main Eligibility/ Exclusion Criteria:	
Inclusion criteria (Stage 1 and Stage 2)
 
 1. Willing and able to provide signed informed consent. 2. Age \geq 18 years 3. Diagnosis of moderate-to-severe OI based on history of more than 20 fractures in lifetime. 4. Glycine substitution in COL1A1 or COL1A2, or pathogenic variants in CRTAP, PP1B, or LEPRE1 (if genetic information is unavailable at screening, this may be assessed at screening visit on a clinical or research basis) 5. Negative urine pregnancy test and ability to use acceptable birth control method for entire duration of the study (if subject is of child-bearing potential) 6. Males who enroll in the study (and their partners) should agree to use an acceptable form of birth control for the entire duration of the study 
Exclusion criteria (Stage 1 and Stage 2)
 
 1. Long bone fracture less than 3 months of screening. These patients can be rescreened after radiologically documented healing of fracture. If individual sustains fracture in the period after the screening visit but before the day 1 of the trial, rescreening will be allowed after 3 months from the date of the fracture 2. Instrumentation in the lumbosacral (LS) and both hips that prevents reliable bone mineral density (BMD) assessment in at least one site

3. Known unhealed fracture involving a long bone (Nonunion or malunion of greater than 1 year duration will not be considered as unhealed fracture).
4. Vitamin D < 15 ng/dL; rescreening for vitamin D levels will be allowed after supplementation
5. Serum albumin-corrected calcium levels below 8 mg/dL. Rescreening will be allowed after calcium supplementation.
6. Hemoglobin < 10 g/dL
7. Platelet count < 75,000/mm³; rescreening will be allowed to confirm that this is not due to a technical error
8. Prothrombin time/ (PT/INR) international normalized ratio > 1.5 times Upper Limit of Normal (ULN).
9. EKG with QTc of > 450 ms (if QTc is prolonged on one EKG, repeat EKG may be done at the same visit for confirmation, if subsequent EKG shows QTc < 450 ms, subject will be eligible for enrollment)
10. Clinical or laboratory abnormality of Grade III or higher as assessed by CTCAE v4.0 which in the view of investigator would compromise safety
11. History of known allergy or hypersensitivity to fresolimumab

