4.2 Exclusion criteria (Stage 1 and Stage 2)

1. Long bone fracture less than 3 months of screening. These patients can be rescreened after radiologically documented healing of fracture. If an individual sustains a fracture in the period after the screening visit but before the day 1 of the trial, rescreening will be allowed after 3 months from the date of the fracture.
2. Instrumentation in the lumbosacral (LS) and both hips that prevents reliable bone mineral density (BMD) assessment in at least one site.
3. Known unhealed fracture involving a long bone (Nonunion or malunion of greater than 1 year duration will not be considered as unhealed fracture).
4. Vitamin D < 15 ng/dL; rescreening for vitamin D levels will be allowed after supplementation.
5. Serum albumin-corrected calcium levels below 8 mg/dL. Rescreening will be allowed after calcium supplementation.
6. Hemoglobin < 10 g/dL.
7. Platelet count $< 75,000\text{mm}^3$; rescreening will be allowed to confirm that this is not due to a technical error.
8. Prothrombin time/(PT/INR) international normalized ratio > 1.5 times Upper Limit of Normal (ULN).
9. EKG with QTc of > 450 ms (if QTc is prolonged on one EKG, repeat EKG may be done at the same visit for confirmation, if subsequent EKG shows QTc < 450 ms, subject will be eligible for enrollment.)
10. Clinical or laboratory abnormality of Grade III or higher as assessed by CTCAE v4.0 which in the view of investigator would compromise safety.
11. History of known allergy or hypersensitivity to fresolimumab.

12. Current clinically significant infection. Rescreening will be allowed after resolution of infection.
13. Personal history of basal cell carcinoma, squamous cell carcinoma or keratoacanthomas.
14. Any personal history of cancer, recent or remote.
15. Any personal history of precancerous condition or lesions including actinic keratosis, atypical moles, Barret's esophagus, or cervical intraepithelial cancer.
16. Evidence of untreated cavities or planned invasive dental work during the study period.
17. Any history of organ transplantation.

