4.7 Single Dose Administration Study (Stage 1)

Primary objective

1. Pharmacokinetics of fresolimumab with a single dose administration
2. To evaluate the safety of a single dose administration of fresolimumab in adults with moderate-to-severe OI with respect to:
 - Vital signs - heart rate, blood pressure, respiratory rate, and body temperature.
 - Laboratory variables.
 - EKG (Corrected QT interval).
 - Adverse events and serious adverse events.

Secondary Objectives

Effect of fresolimumab with respect to:

- Markers of bone turnover in blood (type 1 procollagen, N-terminal or P1NP, Osteocalcin or Ocn, and C-terminal telopeptide or CTX).
- Areal bone mineral density (aBMD) at the hip or the lumbar spine as measured by dual-energy X-ray absorptiometry (DXA) scan.

Dose

- 4 subjects will receive a single intravenous infusion of fresolimumab at a dose of 1 mg/kg body weight. Maximal body weight used for calculation of the drug dose

is 80 kg; for those weighing greater than 80 kg, the drug dose will be calculated using a weight of 80 kg. Total duration of study participation per subject is 6 months.

- 4 subjects will receive a single intravenous infusion of fresolimumab at a dose of 4 mg/kg body weight. Maximal body weight for calculation of the drug dose is 80 kg; for those weighing greater than 80 kg, the drug dose will be calculated using a weight of 80 kg. Total duration of study participation per subject is 6 months.

The two doses have been selected based on safety data from previous studies conducted with fresolimumab that have shown that single doses up to 4 mg/kg have been well tolerated.

Study Procedures

This study will require six visits at a participating clinical site of the BBD consortium. Laboratory tests, ECGs, and radiographs obtained during this study will be interpreted locally by the PIs.

A patient can be enrolled in the study only after an in-person screening visit which will be conducted at BCM. Day 1 visit, during which the participant will receive the study medication will have to be an in-person visit at BCM. Participants are expected to come in for the follow up visits to the study site at BCM. However if there are unforeseen circumstances, or safety reasons (e.g., COVID-19) due to which a participant is unable to travel to BCM, for the follow up visits, an attempt will be made to accommodate study procedures virtually and/or at a remote site which is close to the place of the residence.

Screening visit procedures

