- Obtain informed consent.
- Record medical history.
- Determine if participant has used or is using an exclusionary medication.
- Determine if participant plans to have invasive dental work or skeletal surgery during the period of the study.
- Perform physical examination.
- Measure vital signs - heart rate, blood pressure, respiratory rate, and body temperature.
- Measure height and weight.
- Collect blood sample for laboratory tests (Safety: comprehensive metabolic panel (CMP), complete blood count (CBC), PT/INR, vitamin D testing, bone remodeling markers [serum C-terminal telopeptide of type 1 collagen (CTX), Osteocalcin (Ocn), and amino-terminal propeptide of type I collagen (P1NP)], and lymphoblast culture).
- Confirm that the subject has a genetic test demonstrating that s/he has a Glycine substitution in *COL1A1* or *COL1A2*, or pathogenic variants in *CRTAP*, *PPIB*, or *LEPRE1*. If not present, collect sample for DNA testing.
- Collect urine sample for laboratory test (Safety: urinalysis OR urine dipstick, urine pregnancy test for women of child-bearing age).
- Perform skeletal survey (if historical x-rays are not available to review and ascertain the bony deformities or scoliosis).
- Perform a 12-lead EKG.

- Perform tuberculosis screening by a positive purified protein derivative (PPD) test or Interferon-gamma release assay.

Prior to enrollment (Day 1) screening eligibility criteria for each subject will be reviewed by participating investigators. Individuals who meet the criteria for enrollment will have Study Visit 1 within 60 days of screening.

Day 1 visit procedures (Baseline)

- Review and confirm that the subject meets all criteria for inclusion.
- Confirm that the subject would not be excluded based on screening laboratory tests, a clinically significant infection, a recent fracture or use of any medications since the screening visit that would exclude them from participation.
- Measure vital signs - heart rate, blood pressure, respiratory rate, and body temperature.
- Collect urine from female subjects to determine pregnancy status.
- Perform DXA scan of the lumbar spine (test may not be performed if there is significant scoliosis or the patient has had spinal instrumentation).
- Perform DXA scan total hip and femoral neck (test may not be performed if there are pins or rods in the region of interest).
- Collect blood for pharmacokinetics prior to infusion of fresolimumab
- Intravenous Infusion of fresolimumab over 30 minutes.

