All laboratory testing will be performed using local laboratories and will be interpreted by the respective PIs.

NIH APPROVED

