4.10 Schedule of Events

Procedures	Screening	Treatment				
		1	15	30	90	180
	-60 d window	±3 d window		±7 d window		
Informed Consent	X					
Medical History	X					
Physical Examination	X		X	X	X	X
Vital signs - heart rate, blood pressure, respiratory rate, and body temperature	X	X	X	X	X	X
Height	X					
Weight	X					
Blood/Urine for Safety labs (CBC, CMP, PT/INR, Urinalysis OR Urine Dipstick)	X		X	X	X	X
Blood for Bone remodeling markers (P1NP, Osteocalcin, CTX)	X			X	X	X
Blood for Vitamin D testing	X					
Blood for lymphoblast culture	X			X		
Urine Pregnancy test (if applicable)	X	X				X
Blood for Genetic Testing for COL1A1 , COL1A2 , CRTAP , P3H1 , or PP1B mutations ^a	X					
Skeletal survey ^b	X					
12 Lead EKG	X		X			X
DXA Lumbar Spine ^c		X				X
DXA total hip and femoral neck ^a		X				X
Infusion of fresolimumab		X				
Pharmacokinetics		X ^e	X	X	X	X
Adverse event documentation		X	X	X	X	X

a Genetic testing will be done only if the genotype is not known

b If skeletal films are available for review to ascertain the bony deformities or scoliosis, this test will not be done

c Test may not be performed if there is significant scoliosis or the patient has had spinal instrumentation

d Test may not be done if there are pins or rods in the region of interest

e For Day 1 of the study, PK samples will be obtained prior to the infusion of fresolimumab and after the end of the infusion.

Repeat Dose Administration (Stage 2)							
Procedures	Screening	Treatment					
		1	15	30	90	180	270
	- 60 d window	±3 d window		± 14 d window			
Informed Consent	X						
Medical History	X						
Physical Examination	X		X	X	X	X	X
Vital signs - heart rate, blood pressure, respiratory rate, and body temperature	X	X	X	X	X	X	X
Height	X						X
Weight	X						X
Arm-span	X						X
Blood/urine for Safety labs (CBC, CMP, PT/INR, Urinalysis OR Urine	X		X	X	X	X	X
Blood for Vitamin D testing	X						
Bone remodeling markers (P1NP, Ocn, CTX)	X			X	X	X	X
Blood for PK ^a		X	X	X	X	X	X
Blood for lymphoblast culture	X		X	X	X		X
Blood for Antibody/Immunogenicity testing		X	X	X	X	X	X
Blood for Genetic Testing for COL1A1, COL1A2, CRTAP, P3H1,	X						
Urine Pregnancy test (if applicable)	X	X			X	X	X
Skeletal survey ^b	X						
12-lead EKG	X		X		X		X
Infusion of fresolimumab		X			X ^f	X	X ^f
DXA Lumbar Spine ^c		X					X
DXA total hip and femoral neck ^a		X					X
Peripheral quantitative CT (pQCT) of the forearm ^e		X					X
NRS		X			X	X	X
PROMIS® 29 QOL		X			X		X

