5.10 Quality Control: Study Related Procedures

Accurate, consistent and reliable data will be ensured through the use of standard practices and procedures. The DMCC will audit the Investigators' source data against eCRF entries and verify that the data are accurate.

6. Statistical Considerations

This study is designed to assess the safety and tolerability of fresolimumab in patients with Osteogenesis Imperfecta.

Sample Size: No formal sample size calculations were done for this study. The sample size was selected to allow for an initial assessment of safety in this population and dose range and feasibility of enrollment in this rare disorder. The sample size is 8 for the single dose study and 8 for the repeat dose study. The overall enrollment will be 16.

If needed, 2 additional patients will be enrolled in the repeat dose study to account for a drop-out rate of 20%.

Treatment-Related Adverse Events will be summarized by dose groups. Changes in vital signs, EKG, shifts in laboratory assessments and physical examinations, and patient-reported symptoms will be described. These will assess the primary endpoint of safety. Percent change in bone remodeling markers will be analyzed using a mixed model. BMD in the lumbar spine and the hip at 6 months for single dose study and 12 months for the multiple dose study will be compared to pretreatment levels using a Wilcoxon Signed Rank test. Percent change in the variables of the pulmonary function tests, and change in the 6-minute walk tests, and Numeric Rating Scale (NRS) for pain will be evaluated by Wilcoxon Signed Rank test. Values for derived pharmacokinetic variables, including Cmax, area under the curve, distribution, half-life (T1/2a), elimination half-life (T1/2b), clearance (CL), and volume of distribution at steady state (Vss), will be calculated as previously described and summarized by dose-group using descriptive statistics.

7. Data Management

The results from Screening and data collected during the study will be recorded in the

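### The vitamin D exclusion is printed in ng/dL; read as 25-hydroxyvitamin D it equals 0.15 ng/mL and would exclude essentially no one

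*Combined protocol and SAP*

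**What the plan says.** Section 4.2, item 4, which applies to both stages, excludes candidates with "Vitamin D < 15 ng/dL; rescreening for vitamin D levels will be allowed after supplementation". Exclusion 4 in the synopsis (section 1) and item 2 of section 4.3 (Rescreening) give the same threshold, "Vitamin D < 15 ng/dL", with the same supplement-and-rescreen provision. No section gives a different unit.

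The metabolite is not identified. The Stage 1 screening list in section 4.7 has only "PT/INR, vitamin D testing, bone remodeling markers", the Stage 2 list in section 4.8 is no more specific, and both schedules in section 4.10 say "Blood for Vitamin D testing", marked at screening only. There is no reference range that would settle the unit. Section 4.9 states that "All laboratory testing will be performed using local laboratories and will be interpreted by the respective PIs".

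The bone endpoints are secondary. Section 6 analyses percent change in the remodeling markers with a mixed model. It says that lumbar spine and hip BMD "will be compared to pretreatment levels using a Wilcoxon Signed Rank test". Section 4 describes the groups, and every participant receives fresolimumab.

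**The concern.** The supplement-and-rescreen provision shows that the authors expected some candidates to fail this criterion because of a correctable deficiency. That fits 25-hydroxyvitamin D, although the text does not say so. On that reading the printed threshold is so low that nobody would meet it, and the rescreening route written into three sections would never be used.

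Within each stage the screening value is the only vitamin D measurement. If the criterion does not work, nothing else in the plan detects deficiency directly. Bone markers and BMD are then compared with each participant's own baseline and without an untreated group, so a deficiency present at entry, or corrected during the study, could not be told apart from a drug effect. The plan does not state that this is why the criterion exists; that is an inference from the criterion and the endpoints.

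The printed unit also has a formal role. Under section 7.1 the site attests eligibility against the protocol criteria, and under section 7.5 eligibility violations are recorded and summarized. Read literally, enrolling someone at 8 ng/mL is compliant, and holding that person back for supplementation has no basis in item 4.

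**Working it through.** **Inputs from the documents.** Cut-off 15 ng/dL (synopsis; sections 4.2 and 4.3). Planned enrollment 16 (section 6). The plan has no derived figure to reproduce here; the check is a unit conversion followed by an illustration.

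**Conversion.** 1 dL = 100 mL, so

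15 ng/dL ÷ 100 = 0.15 ng/mL = 150 pg/mL.

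The same numeral in ng/mL would be 15 × 100 = 1500 ng/dL. The ratio is 1500/15 = 100. This step needs no assumption.

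**Share of candidates excluded (assumed distribution).** The documents give no vitamin D levels for this population. Assume that 25-hydroxyvitamin D is log-normal with median *m* and log-scale standard deviation *s*. For a cut-off *c*,

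P(X < c) = Φ( ln(c/m) / s ).

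As printed, c = 0.15 ng/mL:

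| m (ng/mL) | s | ln(c/m)/s | P(X < 0.15) |
|---|---|---|---|
| 15 | 0.6 | −4.605/0.6 = −7.68 | 8 × 10⁻¹⁵ |
| 30 | 0.4 | −5.298/0.4 = −13.25 | 2 × 10⁻⁴⁰ |
| 5 (stress case) | 0.8 | −3.507/0.8 = −4.38 | 5.9 × 10⁻⁶ |

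As probably intended, c = 15 ng/mL:

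| m (ng/mL) | s | P(X < 15) | Expected per 16 screened |
|---|---|---|---|
| 30 | 0.4 | 0.042 | 0.7 |
| 30 | 0.6 | 0.124 | 2.0 |
| 20 | 0.4 | 0.236 | 3.8 |
| 20 | 0.6 | 0.316 | 5.1 |
| 15 | any | 0.500 | 8.0 |

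**Sensitivity.** A second set of assumptions, with median 10 to 30 ng/mL and geometric SD 1.4 to 2.0, gives at most 7 × 10⁻¹⁰ below 0.15 ng/mL (at median 10, geometric SD 2.0). Between 2% and 89% fall below 15 ng/mL. The share caught by a 15 ng/mL rule therefore depends heavily on the assumed distribution. The near-zero share caught by the printed rule does not, because 0.15 ng/mL is about 70 to 200 times below these medians (10/0.15 = 67; 30/0.15 = 200).

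**The other analyte.** If 1,25-dihydroxyvitamin D were meant, the cut-off would be 150 pg/mL and the tables above would not apply.

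**The case against.** The strongest reply is that the documents show only an unnamed analyte with a doubtful unit, which calls for clarification and does not establish an error. The statement that nobody would be excluded depends on vitamin D levels lying in the tens of ng/mL, a scale that appears nowhere in the documents. The tail probabilities describe an assumed distribution; the factor of 100 is the only magnitude that comes from the plan. This is fair. It is why the conclusion is conditional on 25-hydroxyvitamin D and why the percentages are illustrations only.

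The second reply is that the criterion would rarely be applied mechanically. Investigators experienced in osteogenesis imperfecta interpret the laboratory results and review eligibility before Day 1. Screening is also centralised: "A patient can be enrolled in the study only after an in-person screening visit which will be conducted at BCM". One team would probably read ng/mL and do so consistently. This also stands, and it limits the practical effect. It does not make the printed threshold right, since the site attests to the criteria as written.

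Third, related mineral checks exist. Exclusion 5 covers low albumin-corrected calcium, with its own rescreening route, and the metabolic panel is repeated after dosing. These soften the consequence, but they do not measure vitamin D and cannot replace the criterion.

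**Conclusion.** The point holds, as a minor one. The cut-off and unit are the same in all three places and corrected nowhere, so a one-off slip is unlikely. If the analyte is 25-hydroxyvitamin D, as the supplementation route implies, the threshold is 0.15 ng/mL and cannot do its evident job of identifying correctable deficiency. The factor of 100 is exact. That essentially no one would be excluded rests on an assumed distribution, but it survives every version tried, including a stress case of about 6 per million.

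The reach is limited to eligibility and, through it, the secondary bone endpoints. The primary safety outcomes and Stage 1 pharmacokinetics are unaffected, and no size of bias in bone markers or BMD is claimed. Confidence is medium, because the analyte is inferred and the site may well apply the rule in ng/mL anyway.

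**What to change.** The sponsor should confirm the intended analyte and value. Then amend the synopsis (exclusion 4), section 4.2 (item 4) and section 4.3 (item 2) to read, for example, *25-hydroxyvitamin D < 15 ng/mL*, keeping the existing rescreening provision. Name the same analyte in the vitamin D row of both schedules in section 4.10.

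The cost is a few words in three places, the analyte name in two schedule rows and one confirmation from the sponsor. Visits, samples and analyses stay as they are.

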12. Current clinically significant infection. Rescreening will be allowed after resolution of infection.
13. Personal history of basal cell carcinoma, squamous cell carcinoma or keratoacanthomas
14. Any personal history of cancer, recent or remote
15. Any personal history of precancerous condition or lesions including actinic keratosis, atypical moles, Barret's esophagus, or cervical intraepithelial cancer.
16. Evidence of untreated cavities or planned invasive dental work during the study period.
17. Any history of organ transplantation.
18. Any known or suspected valvular heart disease. (Valvular heart disease will be defined by these criteria: 1) history of hemodynamically significant known valvular stenosis or regurgitation; OR 2) presence of grade 3 or higher cardiac murmur at screening visit; OR 3) any history of valvular replacement; OR 4) echocardiographic evidence of any clinically significant valvular stenosis or regurgitation). Trace or trivial valvular regurgitation will not be considered as an exclusion criterion.
19. Anticipated skeletal surgery in the study period.
20. Osteotomy less than 5 months of screening.
21. Prior treatment with zoledronic acid or pamidronate less than 12 months of screening OR oral bisphosphonates less than 6 months of screening OR teriparatide less than one year of screening.
22. Active treatment with systemic glucocorticoids (equivalent of greater than 5 mg of prednisone per day for more than 2 weeks) 3 weeks before screening visit or anticipated treatment of greater than 2 week duration during the study period.
23. Current and daily treatment with antiplatelet agents (aspirin, clopidogrel, dipyridamole, cilostazol, or ticlopidine)
24. Current treatment with anticoagulant medications (low molecular weight heparin analogues, warfarin, dabigatran, rivaroxaban, apixaban, or edoxaban)
25. Documented history of autoimmune disease or immune deficiency. Hashimoto's thyroiditis will not be considered as an exclusion.
26. Evidence of latent tuberculosis by a positive purified protein derivative (PPD) test or Interferon-gamma release assay.
27. Currently receiving another investigational agent in a research study, or less than 30 days since ending treatment on another

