3.2 Current Therapies Available

The current medical therapy for OI is limited to medications that are FDA-approved for treatment of osteoporosis. Bisphosphonates (BPNs), a class of antiresorptive medications, are generally considered as standard of care. The rationale for BPN therapy in OI is that this could increase the bone mineral density, and the increased bone mass albeit with abnormal matrix could potentially reduce fracture rates. Bisphosphonates increase bone mineral density in children and adults with OI; however, their efficacy in reducing fractures is still unclear, particularly in adult patients.^{10,11} More recently, human and murine studies have raised concerns that long-term use of BPNs in OI could result in impaired bone quality and adverse effects such as atypical fractures.¹²⁻¹⁴ An alternative approach to increase bone density and bone quality is the use of bone anabolic agents. A recent trial with teriparatide, a

bone anabolic agent approved for treatment of osteoporosis, showed that efficacy of such therapy is rather limited in those who need therapy the most, i.e., individuals with moderate-to-severe OI.¹⁵ Thus, the current strategy of repurposing approved anti-osteoporotic medications for OI has significant limitations as these do not target the primary pathogenetic mechanisms involved in the causation of bone fragility. Additionally, none of the current therapies are geared towards treatment of extraskeletal manifestations such as pulmonary disease. Currently, there are no disease-specific therapies for OI, and availability of such modalities would be of significant importance to patients.

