18. Any known or suspected valvular heart disease. (Valvular heart disease will be defined by these criteria: 1) history of hemodynamically significant known valvular stenosis or regurgitation; OR 2) presence of grade 3 or higher cardiac murmur at screening visit; OR 3) any history of valvular replacement; OR 4) echocardiographic evidence of any clinically significant valvular stenosis or regurgitation). Trace or trivial valvular regurgitation will not be considered as an exclusion criterion.
19. Anticipated skeletal surgery in the study period.
20. Osteotomy less than 5 months of screening.
21. Prior treatment with zoledronic acid or pamidronate less than 12 months of screening OR oral bisphosphonates less than 6 months of screening OR teriparatide less than one year of screening.
22. Active treatment with systemic glucocorticoids (equivalent of greater than 5 mg of prednisone per day for more than 2 weeks) 3 weeks before screening visit or anticipated treatment of greater than 2 week duration during the study period.
23. Current and daily treatment with antiplatelet agents (aspirin, clopidogrel, dipyridamole, cilostazol, or ticlopidine)
24. Current treatment with anticoagulant medications (low molecular weight heparin analogues, warfarin, dabigatran, rivaroxaban, apixaban, or edoxaban)
25. Documented history of autoimmune disease or immune deficiency. Hashimoto's thyroiditis will not be considered as an exclusion.
26. Evidence of latent tuberculosis by a positive purified protein derivative (PPD) test or Interferon-gamma release assay.
27. Currently receiving another investigational agent in a research study, or less than 30 days since ending treatment on another investigational drug study.
28. Current or planned pregnancy at any time during the study period.
29. Nursing mothers.
30. In the opinion of the investigator, inability to fully comply with the study requirements or participation in the study exposes the subject to undue risk.

Women

If the subject is a female, she will be asked about her menstrual cycle history (including date of last period; menses regularity; typical duration and normalcy; any abnormal discharges; and excessive bleeding). If she is of childbearing potential and is sexually active, she must be non-lactating and have a negative urine pregnancy test at Screening and Baseline/Day1. The subject must agree to use one of these acceptable methods of contraception until study termination:

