4.8 Repeat Dose Administration study (Stage 2)

Primary objective

To evaluate the safety of repeat dose administrations of fresolimumab in adults with moderate-to-severe OI with respect to:

- Vital signs - heart rate, blood pressure, respiratory rate, and body temperature.
- Laboratory variables.
- EKG.
- Adverse events and serious adverse events.

Secondary Objectives

Effect of fresolimumab with respect to:

- Markers of bone turnover in blood (type 1 procollagen, N-terminal or P1NP, Osteocalcin or Ocn, and C-terminal telopeptide or CTX).
- Areal bone mineral density (aBMD) at the hip or the lumbar spine as measured by dual-energy X-ray absorptiometry (DXA) scan.
- Bone density and estimated strength by pQCT of forearm.
- Pain score as assessed by Numeric Rating Scale (NRS).

- Forced expiratory volume in 1 second (FEV1), forced vital capacity (FVC) as measured by pulmonary function tests
- QOL as assessed by PROMIS®.
- Functional capacity as assessed by the 6-minute walk test.

Dose

Group 1

- 4 subjects receive four intravenous infusions of fresolimumab- months 0, 3, 6, and 9, with a follow up period of 3 months (total duration of study participation 12 months).

Group 2

- 4 subjects receive two intravenous infusions of fresolimumab- months 0 and 6, with a follow up period of 6 months (total duration of study participation 12 months).

The dose regimen has been selected based on the duration of bone remodeling cycle that can vary from 3-6 months. The dose regimen and duration are similar to studies that have been conducted with denosumab (Prolia ®), a monoclonal antibody that inhibits receptor activator of nuclear factor kappa-B ligand (RANKL), which has been approved for the treatment of osteoporosis.²⁴ Repeat doses of both 1 mg/kg and 4 mg/kg body weight of fresolimumab, have been studied in a trial titled “A Phase 2, Multicenter, Double-Blind, Parallel Dosing, Randomized Study of Fresolimumab or Placebo in Patients with Steroid-Resistant Primary Focal Segmental Glomerulosclerosis” under IND 100054. This study had four monthly IV administrations of fresolimumab at either 1 mg/kg or 4 mg/kg or placebo with treatment duration of 12 weeks and observation duration of 24 weeks after last dose of study medication. The dose and the number of doses being proposed for our study are similar but far less frequent than used in the study under IND 100054.

Study Procedures

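### Exclusion 21 sets washouts for bisphosphonates and teriparatide but omits denosumab, so a recent user's residual drug effect could not be separated from fresolimumab's on the secondary bone endpoints

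*Combined protocol and SAP*

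**What the plan says.** Item 21 of Section 4.2 is the criterion that deals with earlier osteoporosis drugs. It opens "Prior treatment with zoledronic acid or pamidronate less than 12 months of screening" and continues "OR oral bisphosphonates less than 6 months of screening OR teriparatide less than one year of screening". The synopsis carries the same list. Denosumab is in neither copy.

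Denosumab does appear in Section 4.8, where the Stage 2 schedule is justified: "The dose regimen and duration are similar to studies that have been conducted with denosumab (Prolia ®), a monoclonal antibody", and it is described there as a drug "which has been approved for the treatment of osteoporosis". Section 3.2 gives the treatment background: "The current medical therapy for OI is limited to medications that are FDA-approved for treatment of osteoporosis".

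Screening in both stages includes the step "Determine if participant has used or is using an exclusionary medication". The Day 1 visit repeats the check for drugs taken since screening. Neither step names a drug.

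Section 6 analyses percent change in the turnover markers with a mixed model. It compares BMD with the pretreatment value by a Wilcoxon signed-rank test, at 6 months in Stage 1 and at 12 months in Stage 2. Under Section 4, every participant receives fresolimumab: Stage 1 has two dose groups without randomization, and Stage 2 randomizes only between two infusion schedules.

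**The concern.** The purpose of a washout in this design is to make each participant's pretreatment value a fair reference. No participant goes without fresolimumab, so any other cause of change between baseline and follow-up falls into the same number as the drug effect. Item 21 recognises this for the bisphosphonates and teriparatide. It leaves out the one other drug that the protocol itself describes as approved for osteoporosis, in a population that the protocol says is treated with drugs of that kind.

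If a recent or current denosumab user enrolled, any residual or waning effect of that drug on markers or BMD could not be separated from an effect of fresolimumab. It could look like a benefit or hide one. At stake are the marker and BMD results, which Section 8.2 names as the evidence of benefit to bone. Groups are so small that one person carries real weight in any summary.

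**Working it through.** **1. Does any other criterion close the gap?**
- Item 27 (Section 4.2) covers investigational agents, with a 30-day limit. A prescribed, approved drug is outside it.
- Item 30 rests on the investigator's view of compliance and undue risk, not on carry-over from earlier treatment.
- The screening and Day 1 medication checks (Sections 4.7 and 4.8) refer back to the exclusion list and add nothing to it.

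The omission therefore stands in both copies of the criteria.

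**2. Does the analysis absorb it?** Section 6 states no prior-therapy covariate, stratification or sensitivity analysis. The only marker sample before dosing is the one at screening, up to 60 days before Day 1 (Sections 4.7, 4.8 and 4.10). Drift in that interval would also count as change.

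**3. The plan's own figure.** The only derived design number is the dropout allowance in Stage 2: 8 / (1 − 0.20) = 10, so 2 extra. It reproduces, and this point does not depend on it.

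**4. Shift in a mean.** With k recent users among n participants, each with offset D from the earlier drug, the mean change moves by (k/n) × D.
- Group of 4, one user: 1/4 = 25% of D.
- Stage of 8, one user: 1/8 = 12.5% of D.

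The documents give no D. For illustration only:
- Assumed marker offset of 20% to 100%: 20/4 = 5 to 100/4 = 25 points in a group of 4; 20/8 = 2.5 to 100/8 = 12.5 points in a stage of 8.
- Assumed BMD offset of 2% to 5%, in either direction: 2/4 = 0.5 to 5/4 = 1.25 points in a group of 4; 2/8 = 0.25 to 5/8 = 0.625 points in a stage of 8.

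**5. Effect on the signed-rank test.** The plan states no significance level; 0.05 two-sided is assumed here. With n = 4 the smallest two-sided p is 2/2^4 = 0.125, so the test cannot reach 0.05. With n = 8 the smallest is 2/2^8 = 0.0078, and the exact size at 0.05 is 2 × 5/256 = 3.9%. The table gives simulated rejection rates for n = 8 with no fresolimumab effect, normally distributed changes, all offsets in the same direction and 20,000 runs per setting.

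| Recent users among 8 | Offset 1 SD | Offset 2 SD | Offset 3 SD |
|---|---|---|---|
| 0 | 3.8% | 4.2% | 4.0% |
| 1 | 3.8% | 3.7% | 3.8% |
| 2 | 5.5% | 7.1% | 7.9% |
| 3 | 8.4% | 13.8% | 15.4% |
| 4 | 13.4% | 26.1% | 30.8% |

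The zero-user row differs across columns only by simulation noise. One user leaves the rate where it was; it rises only from two users on. With 10 participants the pattern is the same: 4.9% to 5.2% with none and 4.6% to 4.9% with one. The mixed model for the markers was not simulated. The mean shift in step 4 is the guide there.

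**6. Use during the study.** Item 21 concerns prior treatment only, whereas item 22 covers both earlier and anticipated glucocorticoids. Section 7.5 has a deviation category for excluded medications, but the plan gives no list of bone drugs to which it would apply on study.

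**The case against.** The strongest reply is that the protocol nowhere says adults with OI receive denosumab. Section 3.2 discusses bisphosphonates and teriparatide, and item 21 covers both. Denosumab enters only as an analogy for the dosing interval. This stands as a limit on likelihood: the general sentence in Section 3.2 makes prior use plausible, but the documents do not say how common it is.

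A second reply is that the size, timing and direction of a denosumab offset come from outside the documents. That stands too, so the point values above are illustrations. What the documents do support is that the two effects could not be told apart.

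A third is that before-after comparisons without a control are weak in any case, and naming one drug does not cure that. This is true, but the plan already chose washouts as its protection, and the list has a gap.

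A reader might infer that the plan should bar every bone-active agent, before and during the study. The documents do not support that. The term is undefined and could reach vitamin D and calcium, after which Section 4.3 allows rescreening. A rule on treatment during the study is also a clinical decision for the sponsor.

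**Conclusion.** The point holds as a gap in eligibility with a bounded consequence. As written, item 21 admits a recent or current denosumab user, and neither the design nor Section 6 can separate that person's residual drug effect from a fresolimumab effect. One user moves a mean by 25% of the personal offset in a group of 4, or 12.5% in a stage of 8.

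Three stronger conclusions are tempting and do not follow:
- That an offset would be reported as a fresolimumab effect. This needs such a person to enrol, and the effect could as well be masked.
- That the BMD test becomes unreliable. One user in 8 leaves its false-positive rate at about 4%; the distortion lies in means and percent-change summaries.
- That the trial's main conclusion is at risk. The primary outcomes are safety and, in Stage 1, pharmacokinetics; only the secondary bone endpoints are directly affected.

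The verdict assumes that enrolment follows the written criteria and that no prior-therapy adjustment is specified elsewhere.

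**What to change.** This is a cheap improvement.

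- Reconcile item 21, in Section 4.2 and in the synopsis, with Sections 3.2 and 4.8 by adding prior denosumab, with a washout the sponsor sets.
- Record prior bone therapy (drug and date of last dose) for every participant, and state in Section 6 that marker and BMD results will be reported with and without any recent users.
- Reconcile item 21, which covers only prior treatment, with the excluded-medication deviations in Section 7.5, so that it is clear what the category refers to for bone drugs.

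The cost is a few lines of text, one data field and one extra presentation of the results. The planned numbers stay at 8 + 8, or 8 + 10 with the dropout allowance. The downside is a possibly slightly smaller eligible pool in a rare disorder.
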